8 ASSESSMENT OF SAFETY

8.1 Assessing and Recording Safety Parameters

Regulatory requirements including FDA regulations, ICH Guidelines for GCP, and European Union Clinical Trials Directive set forth safety monitoring and reporting responsibilities of the Sponsors and Site PI to ensure the safety and protection of human subjects participating in clinical trials.

Responsibilities

Site PIs participating in this trial are responsible for and will:

- Evaluate subject safety including assessment of AEs for seriousness, severity, and causality;
- notify the Sponsor of SAEs immediately;
- provide detailed written reports, including necessary documentation requested by the Sponsor or IRB/IEC, promptly following immediate initial reports;
- inform the IRB/IEC of AEs as requested by applicable regulatory requirements.

8.1.1 Adverse Events

ICH E6 defines an AE as any untoward medical occurrence in a patient or clinical investigation subject administered a pharmaceutical product regardless of its causal relationship to the study treatment. FDA defines an AE as any untoward medical occurrence associated with the use of a drug in humans, whether or not considered drug-related.

An AE can therefore be any unfavorable and unintended sign (including an abnormal laboratory finding), symptom, or disease temporally associated with the use of medicinal (investigational) product. The occurrence of an AE may come to the attention of study personnel during study visits and interviews of a study recipient presenting for medical care, or upon review by a study monitor.

All AEs, including solicited local (injection site), starting from administration of the first dose of study drug until the final study visit will be captured on the appropriate data DCF and eCRF. Information to be collected for AEs includes event description, date of onset, assessment of

severity, relationship to study product, and alternate etiology (assessed only by those with the training and authority to make a diagnosis and listed on Form FDA 1572 as a PI), date of resolution, seriousness and outcome. AEs occurring during the trial collection and reporting period will be documented appropriately regardless of relationship. AEs will be followed through resolution or until assessed to be stable by the PI.

Any medical condition that is present at the time that the subject is screened will be considered as baseline and not reported as an AE. However, if the severity of any pre-existing medical condition increases, it should be recorded as an AE.

Adverse Events Grading

All AEs (laboratory and clinical symptoms) will be graded for severity and assessed for relationship to study product (see definitions). Abnormalities present at baseline will not be reported as AEs unless worsening in severity post-dosing. AEs characterized as intermittent require documentation of onset and duration of each episode. The start and stop date of each reported AE will be recorded on the appropriate DCF and eCRF. For vital sign AEs, when multiple readings are taken within the same day the AE of highest severity will be documented to allow an assessment of the duration of the AE from the highest level of intensity. If a subject was enrolled in the trial with a laboratory value that is outside the reference range, but within the acceptable ranges, an AE will be recorded if it otherwise meets the definition of AE in [Section 8.1.1](#) and the on-study value is higher (if initially high) or lower (if initially low) than the screening value.

Severity of Event:

AEs will be assessed by the Site PI using a protocol-defined grading system ([Appendix B](#)). For events not included in the protocol-defined grading system, the following guidelines will be used to quantify severity:

Mild (Grade 1): Events that are usually transient and may require only minimal or no treatment or therapeutic intervention and generally do not interfere with the subject's usual activities of daily living,

Moderate (Grade 2): Events that are usually alleviated with additional specific therapeutic intervention. The event interferes with usual activities of daily living, causing discomfort but poses no significant or permanent risk of harm to the subject,

Severe (Grade 3): Events interrupt usual activities of daily living, or significantly affects clinical status, or may require intensive therapeutic intervention. Severe events are usually incapacitating.

Relationship to Study Product: The assessment of the AE's relationship to study product will be done by the licensed study physician indicated on Form FDA 1572 and the assessment will be part of the documentation process. Whether the AE is related or not, is not a factor in determining what is or is not reported in this trial. If there is any doubt as to whether a clinical observation is an AE, the event should be reported.

In a clinical trial, the study product must always be suspect. The relationship to study product will be assessed for AEs using the terms related or not related:

Related – There is a reasonable possibility that the study product caused the AE. Reasonable possibility means that there is evidence to suggest a causal relationship between the study product and the AE,

Not Related – There is not a reasonable possibility that the administration of the study product caused the AE.

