10.1 Study Hypotheses

The objectives of this trial are to obtain safety, tolerability, and PK data for rezafungin. There are no formal hypotheses being tested in this trial.

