10.5.1 Adverse and Serious Adverse Events

AEs will be coded using Medical Dictionary for Regulatory Activities® (MedDRA). All AEs occurring after study drug dosing will be summarized using frequency counts and percentages. Summaries will be presented by dose cohort and control group. The following summaries will be presented for AEs and SAEs:

- Overall (i.e., regardless of severity or relationship to study drug),
- By severity grade (mild, moderate, or severe),
- By relationship to study drug,
- By MedDRA level hierarchy (system organ class, HLGT and preferred term).

Unless otherwise specified, at each level of subject summarization in reporting the incidence of the AEs, a subject will be counted once if the subject reported one or more AEs. If more than one occurrence of an AE is reported, the AE of the worst severity or the worst-case relationship assessment will be summarized. For crossover data, AEs will be summarized separately for each

treatment and the worst severity and worst-case relationship after each treatment will be summarized. An AE that began after the first treatment, continued into the second period, and worsened in severity after the second treatment will be considered a new AE associated with the second treatment.

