### 7.3.2. Unsolicited Adverse Events

A brief overall summary of AEs by Dose Group including number of subjects with at least one solicited reactogenicity event of any severity, number of subjects with ulceration, number of subjects with at least one AE of any severity, number of subjects with at least one related AE of any severity, and number of subjects with at least one SAE ([Table 8](#)).

All AEs will be presented in listings ([Listing 10](#)). A subject listing of non-serious AEs of moderate or greater severity will also be reported ([Table 15](#)).

The following summaries for unsolicited adverse events will be presented:

- The total number of AEs and the number and proportion of subjects reporting at least one unsolicited AE will be summarized by Dose Group, SOC, and PT. Denominators for percentages are the number of subjects in the Safety Population. A 95% CI will be presented by Dose Group for each SOC and PT ([Table 12](#)).
- The number and proportion of subjects reporting at least one AE, summarized by Dose Group, SOC, PT, maximum severity, and relatedness ([Table 13](#)).
- By Dose Group, bar charts of proportions of subjects with related serious and non-serious AEs by maximum severity and SOC. This figure describes the number of subjects with an event (each subject counted once per SOC) ([Figure 17](#)).

- By Dose Group, bar charts of numbers of related serious and non-serious AEs by severity and SOC. This figure describes the total number of occurrences of each event, including multiple occurrences per subject ([Figure 18](#)).

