**Table 15: Listing of Non-Serious, Unsolicited, Moderate or Severe Adverse Events**

[Implementation Note: This listing is included in the tables document, as it is included in the body of the abbreviated CSR. If the event is ongoing (no stop date), indicate “ongoing” in the “Duration” column. In the “If Not Related, Alternate Etiology” column, merge the 2 data fields for collecting alternate etiology, separate by a colon. Listing should be sorted by Dose Group, Subject ID, and AE Number.]

Adverse Event	MedDRA System Organ Class	MedDRA Preferred Term	Study Day	Duration of AE in Days	Severity	Relationship to Study Treatment (Alternate Etiology)	Action Taken with Study Treatment	Subject Discontinued Due to AE	Outcome
Dose Group: , Subject ID: , AE Number:									
Comments:									
Dose Group: , Subject ID: , AE Number:									
Comments:									

---

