**Figure 17: Proportions of Subjects with Related Adverse Events by Dose Group, MedDRA SOC, and Severity**

[Implementation Note: This figure includes serious and non-serious unsolicited adverse events deemed related to study product. Note that this figure will present the number of subjects with types of adverse events, and a subject may not be counted more than once for the same type of adverse event but will be counted only once for the maximum severity of the respective type. Each figure panel will show counts for all SOCs observed in any Dose Group during the study (as a related AE). If the number of SOCs is too large to fit in 2 rows of panels, then this figure will be split into multiple figures in the CSR, with 1 row of 2 panels in each figure. SOCs will be ordered alphabetically.]

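### The protocol counts solicited injection-site reactions as AEs to be summarised by relationship, but the SAP never shows the relationship or outcome of the non-serious ones and does not declare the restriction

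*Protocol*

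**What the plan says.** **Protocol.** Section 8.1.1 captures "All AEs, including solicited local (injection site), starting from administration of the first dose of study drug until the final study visit". The data items it names for AEs include onset, severity, relationship, resolution date, seriousness and outcome. It adds: "All AEs (laboratory and clinical symptoms) will be graded for severity and assessed for relationship to study product". Section 10.5.1 states: "All AEs occurring after study drug dosing will be summarized using frequency counts and percentages". One of the summaries it lists is "By relationship to study drug", and it makes no exception for solicited events. Section 10.5.3, headed as additional safety analyses, covers local reactogenicity by type, grade, dose group and time point. It also promises a summary of injection-site ulcers by size and resolution. The opening of Section 10 says that departures from the protocol's analysis will be described in the SAP.

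**SAP.** Section 7.3.1 sends solicited local symptoms to Tables 9-11, Figures 2-16 and Listing 9. Section 7.3.2 covers unsolicited AEs. It says of Table 15: "A subject listing of non-serious AEs of moderate or greater severity will also be reported". The title of that shell is "Listing of Non-Serious, Unsolicited, Moderate or Severe Adverse Events". The note to Figure 17, repeated for Figure 18, reads: "This figure includes serious and non-serious unsolicited adverse events deemed related to study product". Table 13 and Listing 10 are unsolicited by title. Section 11 reports only the early termination and the dose groups that remain.

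**The concern.** The protocol's definition of an AE and its promise to summarise all AEs by relationship both reach injection-site reactions. The SAP displays that carry relationship mostly do not. For a subcutaneous product whose repeat-dose monkey study showed adverse injection-site toxicity in every dose group (Protocol 3.1.2), local reactions are the events for which attribution to drug matters most.

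Two things are at stake. First, a reader of the abbreviated CSR who takes the related-AE proportion from Table 13 or Figure 17 would see a figure with the anticipated local events left out, and no note saying so. Second, a non-serious local reaction, even a severe one, would have its relationship and outcome collected but not displayed.

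**Working it through.** The plan has no figure of its own to reproduce: "There are no formal hypotheses being tested in this trial". The check is a comparison of texts and shells, followed by one illustration.

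**Step 1. SAP displays that show relationship (seven).**

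| Display | Scope as written |
|---|---|
| Table 8, related-AE rows | Not stated; the note excludes only laboratory AEs graded by the toxicity tables |
| Table 13 | Unsolicited |
| Table 14 | All SAEs |
| Table 15 | Unsolicited, non-serious, moderate or severe |
| Figures 17 and 18 | Unsolicited, related |
| Listing 10 | Unsolicited |

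Five are expressly unsolicited (Tables 13 and 15, Figures 17 and 18, Listing 10). Two are not (Tables 8 and 14).

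**Step 2. SAP displays of solicited reactions.** Tables 9-11 (3), Figures 2-16 (15) and Listing 9 (1) make 3 + 15 + 1 = 19. None shows relationship or outcome. Apart from dose group and subject, Listing 9 has columns for time point, assessment source, location, symptom, functional grade and measurement with grade.

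**Step 3. Put the two together.** A serious local reaction reaches Table 14, with relationship and outcome. A non-serious one reaches only the 19 solicited displays and, at most, a count in Table 8. Its relationship and outcome have no display of their own.

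**Step 4. Ulcers.** Protocol 10.5.3 asks for size and resolution. The SAP gives a functional grade, a measurement grade, the measurement itself in Listing 9 and a count row in Table 8. It has no resolution field or summary for a solicited ulcer.

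**Step 5. Illustration of size.** Protocol Table 1 plans n = 6 on 10 mg, and SAP 5.1 specifies Wilson intervals. The event counts are hypothetical: 5 subjects react locally, every reaction is judged related, and 1 of the 5 also has an unsolicited related AE. With z = 1.96, z² = 3.8416:

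limits = [x + z²/2 ± z·√(x(n − x)/n + z²/4)] / (n + z²)

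- Counting all AEs, x = 5: [6.9208 ± 1.96·√(0.8333 + 0.9604)] / 9.8416 = 0.703 ± 0.267. So 5/6 = 83%, CI 44% to 97%.
- Unsolicited only, x = 1: [2.9208 ± 1.96·√(0.8333 + 0.9604)] / 9.8416 = 0.297 ± 0.267. So 1/6 = 17%, CI 3% to 56%.

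The gap depends on the assumptions. If no local reaction is judged related, both counts are 1/6. If all six react locally, all are judged related and there is no unsolicited related AE, it is 6/6 (61-100%) against 0/6 (0-39%).

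**The case against.** The best defence is that the protocol itself keeps two data streams. Its endpoints assess tolerability by solicited local reactogenicity, apart from AEs. Section 10.5.3 specifies the reactogenicity analysis without naming relationship, and Section 10.5 leaves details of presentation to the SAP. On that view the SAP merely carries out the split. This makes separate solicited tables reasonable, but 10.5.3 is headed as additional, so it does not withdraw what 10.5.1 promises for all AEs. The SAP also leaves 10.5.3's own ulcer-resolution item unmet.

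A second defence is that the Table 15 sentence sits under a heading for unsolicited AEs, so shell and section agree. That is fair as a reading of the SAP alone. The mismatch that counts is with the protocol.

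Third, this is a terminated, descriptive study with an abbreviated report on two small cohorts. That limits the consequences, but the SAP still presents itself as expanding on the protocol's statistical section, and the change is undeclared.

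A reader might go further and infer that local toxicity is missing from the results, or that a severe local reaction is shown nowhere. The documents do not support that. Tables 9-11 and Listing 9 give severity by dose group, placebo and time point, so persistence can be seen. Table 8 has solicited rows and an ulceration row. Table 14 would show a serious local event in full, and Protocol 8.1.2 names injection-site ulcers as an example of an event that may be serious.

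**Conclusion.** The point holds as a reporting gap. Non-serious solicited local reactions are reported by severity and time but not by relationship or outcome, contrary to Protocol 8.1.1 and 10.5.1 read together. The ulcer-resolution summary is missing, and Section 11 is silent on the restriction.

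In the illustration the gap is 5/6 against 1/6, and it can range from nothing to 6/6 against 0/6. It rests on invented counts and on local reactions being judged related. The lower figure is established only for Table 13 and Figure 17. It should not be read as the SAP's overall related-AE result, because Table 8's rows for any AE, related AE and AE leading to early termination are ambiguous: their placement suggests unsolicited events, while the note excludes only laboratory AEs. Two programmers could code them differently.

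The change should be made. It does not put the separate severity summaries of local reactions in doubt.

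**What to change.** 1. In Table 8, define the rows for any AE, related AE and AE leading to early termination as solicited plus unsolicited. Keep the separate solicited rows.
2. Add an all-AE version of the by-relationship summary (Table 13 and Figures 17-18), or a related/not-related row for solicited local events.
3. Include non-serious moderate or severe solicited reactions in Table 15.
4. Add an event-level listing of solicited reactions with relationship, seriousness, onset, resolution date and outcome, and with ulcer size and resolution as Protocol 10.5.3 promises. Extra columns in Listing 9 would not serve, because it has a row for each symptom and time point, whereas these items belong to an event.
5. Record any restriction that remains, with its reason, in SAP Section 11.

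The cost is SAP wording and minor programming for two small cohorts, on items that Protocol 8.1.1 says are collected. One caution: Listing 9 cites a separate eCRF for solicited reactions, whose fields are not shown. If that form lacks an item, Section 11 should say so. The related-AE percentage may become less favourable.

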10.5.2 Clinical Safety Labs, Vital Signs, and Electrocardiograms

Baseline for clinical safety labs, vital signs, and ECGs will be defined as the last result obtained before the dose of study product. For crossover data, there will be a separate baseline for each treatment. Changes from baseline for clinical safety labs, vital signs, and ECGs results will be summarized by dose group and time point. Clinical safety labs and vital signs will be graded ([Appendix B](#)) and summarized by severity, group, and visit. Rules for analyzing replicates for a safety time point (labs, vital signs, ECG), if obtained, will be described in the SAP.

Treatment-emergent abnormal laboratory test results will be identified. Treatment-emergent abnormal laboratory tests are tests for which the result was not graded as mild or worse at baseline but graded as mild or worse after dosing. Laboratory tests graded as mild at baseline, but moderate or worse any time after dosing will also be regarded as treatment-emergent abnormal laboratory test results.

ECG measurements will include heart rate, RR interval, QT interval, QTcF interval, PR interval, and QRS duration. Baseline for ECG measurements is defined per protocol as the value pre-dosing on Day 1 (or pre-dosing on Day 21 for period 2 of Part 3). Change from baseline will be summarized descriptively by regimen at each scheduled evaluation. QTc results will be summarized categorically according to the ICH Guideline E14 “Clinical Evaluation of QT/QTc Interval Prolongation and Proarrhythmic Potential for Non-Antiarrhythmic Drugs” (October 2005):

- QTcF >450 ms, males only
- QTcF >470 ms, females only
- QTcF >480 ms
- QTcF >500 ms
- QTcF increases from baseline by at least 30 ms but less than 60 ms
- QTcF increases from baseline by at least 60 ms

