##### **3.3.2. Baseline**

For clinical laboratory results, and vital sign (VS) measurements, the baseline assessment is the last measurement recorded prior to dosing, except for height, weight, and BMI, which baseline will be defined as the measurements recorded at the initial Screening Visit. For electrocardiogram (ECG) results, baseline is defined as the median of the triplicate measurements taken within 60 minutes of dosing. If multiple triplicate measurements are taken prior to dosing, the median of last set of triplicates will be used as baseline.

Age will be based on age at enrollment. Age at enrollment is an integer value with units of years and is calculated from the subject’s enrollment date (ENROLLDT) and birth date (BRTHDT) using the following algorithm.

- If month(ENROLLDT) > month(BRTHDT), then AGE = year(ENROLLDT) – year(BRTHDT)
- If month(ENROLLDT) < month(BRTHDT), then AGE = year(ENROLLDT) – year(BRTHDT) – 1
- If month(ENROLLDT) = month(BRTHDT) and day(ENROLLDT) ≥ day(BRTHDT), then AGE = year(ENROLLDT) – year(BRTHDT)
- If month(ENROLLDT) = month(BRTHDT) and day(ENROLLDT) < day(BRTHDT), then AGE = year(ENROLLDT) – year(BRTHDT) – 1

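### For subjects enrolled with an out-of-range laboratory value, Protocol 8.1.1 judges AEs against screening, while Protocol 10.5.2 and the SAP use the last pre-dose result, so some Grade 1 worsening can go unrecorded as an AE

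*Protocol*

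**What the plan says.** Protocol 8.1.1 (Adverse Events Grading) sets a general rule and a special one.

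- General rule: "Abnormalities present at baseline will not be reported as AEs unless worsening in severity post-dosing".
- Special rule, for a subject who entered with a mildly abnormal but tolerated laboratory result. It sets two conditions: the finding must satisfy the section's own AE definition, and the later result must be "higher (if initially high) or lower (if initially low) than the screening value".

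The laboratory analysis sections use a later reference.

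- Protocol 10.5.2: baseline for safety laboratory tests "will be defined as the last result obtained before the dose of study product". Treatment-emergent abnormalities are "tests for which the result was not graded as mild or worse at baseline but graded as mild or worse after dosing", plus those that go from mild to moderate or worse.
- SAP 3.3.2: "the baseline assessment is the last measurement recorded prior to dosing".
- SAP 7.6: a result already abnormal at screening is not reported as an AE unless it is treatment-emergent. For continuous parameters, that means numerically beyond baseline in the relevant direction.

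Screening runs from Day -28 to Day -2 (Protocol 6.2). A further set of laboratory samples, labelled baseline, is drawn on Day -1 (Protocol 6.3). Unless that sample is missing, the screening value is not the last pre-dose value.

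**The concern.** The site decides whether to enter a laboratory AE from 8.1.1; the SAP classifies the same result against a different value. The two references part when a value accepted as mildly abnormal at screening has returned to range by Day -1. If it then becomes abnormal again after dosing without passing the screening value, the analysis sections call it treatment-emergent and 8.1.1 does not call it an AE.

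The general rule does not close this gap. It deals with abnormalities present at baseline, and in this case none was present on Day -1.

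Adverse events and clinical laboratory tests are both primary safety outcomes (Protocol 3.3.1). At stake is whether the AE listing is complete for mild laboratory worsening and agrees with the laboratory tables. The SAP programming cannot restore an AE that the site never entered.

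**Working it through.** The plan gives no figure on this point, so the check compares the rules case by case.

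**Inputs**

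- Male ALT grades (Protocol Appendix B): Grade 1 is 41–100 U/L, Grade 2 is 101–200, Grade 3 is above 200.
- Entry cap: an out-of-range value is acceptable if judged clinically insignificant and not above Grade 1 (Protocol 5.1.2, exclusion 6).

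**Rules**, with S = screening, B = last pre-dose value, P = post-dose value:

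- 8.1.1 comparison, taken alone: P is graded and P > S.
- 10.5.2: B ungraded and P Grade 1 or worse, or B Grade 1 and P Grade 2 or worse.
- SAP 7.6: P is graded and P > B.

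**Cases** (illustrative values, U/L)

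| S | B | P | 8.1.1 | 10.5.2 | SAP 7.6 |
|---|---|---|---|---|---|
| 60 | 38 | 58 | no (58 < 60) | yes (Grade 0 to 1) | yes (58 > 38) |
| 90 | 35 | 85 | no (85 < 90) | yes (Grade 0 to 1) | yes (85 > 35) |
| 60 | 45 | 58 | no (58 < 60) | no (Grade 1 to 1) | yes (58 > 45) |
| 90 | 35 | 120 | yes (120 > 90) | yes (Grade 0 to 2) | yes (120 > 35) |

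The first two rows show the mismatch. The third shows a separate difference: 10.5.2 asks for a change of grade, SAP 7.6 for a numerical change.

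**Upper bound on the grade that can be missed.** Entry requires S ≤ 100. A Grade 2 value has P ≥ 101, so P > S always, and the 8.1.1 comparison is met. Enumerating every whole-number combination of S from 41 to 100, B from 10 to 100 and P from 10 to 300 confirms this: no missed value exceeded Grade 1. The same argument applies to any analyte graded in the direction of its screening abnormality.

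**Halting rules.** The laboratory AE criteria in Protocol 8.7.1 and 8.7.2 need Grade 2 or higher, so the missed values cannot reach them.

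**Order of magnitude, under assumptions only.** The documents give no between-visit correlation. Assume normal values, a reference limit at 1.96 SD, three post-dose samples (Part 1: Days 2, 7 and 30), no drug effect, and a correlation between visits of 0.5, 0.7 or 0.85. Among analytes out of range at screening, simulation gives 12%, 13% and 11% that are in range on Day -1, out of range after dosing, and never beyond screening. About 2.5% of analytes are out of range at screening in a given direction, so per analyte and direction this is 0.025 × 0.11 to 0.13, or roughly 0.3%. The simulation leaves out the Grade 1 cap, the clinical-insignificance judgement, the permitted repeat at screening and removals on Day -1. With no drug effect, every such event in it is ordinary variation.

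**The case against.** The strongest case is that this is an unharmonised convention with little consequence.

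- **The analysis already covers the result.** SAP 7.6 grades against the last pre-dose value, and its toxicity and change tables and listings do not depend on whether the site logged an AE. SAP Table 8 also leaves out laboratory AEs assessed with the toxicity tables. This stands and limits the effect. It does not remove it, because Tables 12 and 13 and Listing 10 state no such exclusion.
- **Screening has some support as a reference.** Protocol 8.1.1 and SAP 7 treat a medical condition present at screening as baseline. That explains the wording, but SAP 7.6 deals specifically with laboratory results abnormal at screening and uses the last pre-dose value.
- **The example depends on a reading.** One could argue that a man in range on Day -1 was not enrolled with an abnormal value, so the general rule applies and the 58 could be recorded. The special rule also says when an AE is recorded, not that none is recorded otherwise. Both are possible, but the rule names the screening value as its reference, and the comparison has no purpose unless it limits recording.
- **The fix is partial.** It aligns the reference but leaves grade change in 10.5.2 beside numerical change in SAP 7.6. This stands.

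A reader might also infer that a rise already present on Day -1 would be recorded as an AE. With ALT 45 at screening, 80 on Day -1 and 75 after dosing, the screening comparison is indeed met. The documents do not support the inference: the result must otherwise meet the AE definition, the general rule requires worsening after dosing, and AE capture runs "starting from administration of the first dose of study drug until the final study visit". Protocol 7.2.1, read literally, would also withdraw that subject on Day -1.

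**Conclusion.** The inconsistency is real and minor. For subjects enrolled with an out-of-range but acceptable laboratory value, 8.1.1 uses a different reference from 10.5.2, SAP 3.3.2 and SAP 7.6. A Grade 1 result that is new since Day -1 can then be left out of the AE record while appearing in the laboratory tables.

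Two wider readings do not hold. The screening comparison does not govern on-study laboratory values in general, since everyone else falls under the general baseline rule. Nor is a serious signal or a halting trigger hidden, since missed values in the same direction cannot exceed Grade 1.

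The logic rests on the documents alone, given the reading that such a subject falls under the special rule. The figure of roughly 0.3% per analyte and direction rests on assumed correlations and indicates scale only. The SAP Preface states that the trial was terminated and that nobody was enrolled beyond SAD Cohorts 1 and 2, so the practical value lies in interpreting the abbreviated report and in any reuse of this text.

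**What to change.** In Protocol 8.1.1, replace the screening value as the reference with the baseline value, defined as the last result before dosing with a pointer to Section 10.5.2. Site recording and the laboratory tables then share one reference. The cost is one phrase and a few more Grade 1 laboratory AEs among subjects whose screening value was abnormal.

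For data already collected, the abbreviated report can state which reference the site used when it entered laboratory AEs.

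Separately, the passages on out-of-range Day -1 results need reconciling. Exclusion 6 in Protocol 5.1.2 and Protocol 6.3 tolerate values judged clinically insignificant (exclusion 6 up to Grade 1), while Protocol 7.2.1 read literally withdraws the subject. The answer determines which subjects can be dosed with an abnormal baseline at all.
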